3.6. Methodology

3.6.1. Investigational Type

19. The current investigation is a feasibility study, to assess the usability of the YE560 option for visualization of FS during VS resection.

20. 3.6.2. Patients

21. A total of 90 consenting patients, either male or female, clinically indicated for surgical resection of suspected VS, meningioma, HNP, HNS or recurrent VS, meningioma, HNP, or HNS will be part of the feasibility study phase. Patients with neurofibromatosis type 2 and those receiving prior radiation therapy will not be excluded from the study.

3.6.3. Timeframe

22. The estimated timeframe for enrollment is approximately 18 months (from January 2019 – June 2021).

3.6.4. Recruitment Process

23. Patients under the care of the Clinical Investigators who are clinically indicated for surgical resection as a suspected VS, meningioma, or head and neck paraganglioma or recurrent VS, meningioma, HNP, or HNS will be considered eligible for participation in the study. Each potential participant will be assessed against the inclusion and exclusion criteria. Potential patients shall be provided with plain language information about the study and will have the opportunity to ask questions of the study investigators. Informed consent shall be obtained by the Principal Investigator or Co-Investigators from eligible patients wishing to participate. Any patient that chooses not to participate in the study will undergo their indicated surgery with standard techniques, and their health care will not be compromised in any way. Patients shall be free to withdraw from the study at any time.

3.6.5. Inclusion Criteria

Inclusion criteria shall be:

- Patient with a suspected VS, meningioma, HNP or HNS
- Recurrent VS, meningioma, HNP, or HNS with prior microsurgical resection or radiation therapy
- Clinical indication for microsurgical resection

3.6.6. Exclusion Criteria

Exclusion criteria shall be:

- Children (patients less than 18 years of age)
- History of allergy to FS
- History of renal failure
- Pregnant women
- Those with inability to give informed consent
- Prisoners and inmates

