4.4. Clinical Indications & Contraindications for use in Study

The clinical indication for use of the YE560 fluorescence module in the proposed study is neurological pathology requiring open craniotomy or translabyrinthine otologic approach.

Use of the YE560 fluorescence option is contra-indicated in patients where the tumor resection bed is not directly surgically exposed and cannot be visualized with the surgical microscope.

A fluorescent contrast agent, FS will be administered intravenously within its labeled dose range for its approved use in ophthalmic applications to reveal fluorescence contrast during the use of YE560.

Occasionally patients may experience adverse events. The fluorescein dye can rarely cause allergic reactions. Fluorescein dye is a FDA-approved medicine that is routinely used by ophthalmologists (eye doctors) to perform exams of the retina of the eye. Administration of Fluorescein is contraindicated in patients with:

- Known allergy or prior adverse reaction to Fluorescein
- Women who are pregnant or breastfeeding

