7.2. Method for Assigning Subjects to Study Group

Patients under the care of the Clinical Investigators who are clinically indicated for surgical resection as a suspected VS or recurrent VS will be considered eligible for participation in the study. Investigators will determine if patients are eligible for the study during clinic appointments. Each potential participant will be assessed against the inclusion and exclusion criteria. Potential participants shall be provided with plain language information about the study on the IRB-approved consent form and will have the opportunity to ask questions of the study investigators. Informed consent shall be obtained by the Principal Investigator, Co-Investigators, or research coordinator from eligible patients wishing to participate. Any patient who chooses not to participate in the study will undergo their indicated microsurgery with standard techniques, and their health care will not be compromised in any way. Participants shall be free to withdraw from the study at any time. Participants will be withdrawn if their intraoperative biopsy yields an entity other than VS.

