2. *Withdrawal of IRB approval.* A Sponsor shall notify FDA and all reviewing IRBs and participating Investigators of any withdrawal of approval of an investigation or a part of an investigation by a reviewing IRB within 5 working days after receipt of the withdrawal of approval.

3. *Withdrawal of FDA approval.* A Sponsor shall notify all reviewing IRBs and participating Investigators of any withdrawal of FDA approval of the investigation, and shall do so within 5 working days after receipt of notice of the withdrawal of approval.

4. *Progress reports.* At regular intervals, and at least yearly, a Sponsor shall submit progress reports to all reviewing IRBs.

APPENDIX 2

Investigator's Agreement and Obligations

Responsibilities of Investigators

General responsibilities of Investigators

An Investigator is responsible for ensuring that an investigation is conducted according to the signed agreement, the investigational plan and applicable FDA regulations, for protecting the rights, safety, and welfare of subjects under the Investigator's care, and for the control of devices under investigation. An Investigator also is responsible for ensuring that informed consent is obtained in accordance with 21 CFR part 50.

Study staff will meet on a quarterly basis to debrief and assess progress, with email contact in the interim as needed. Meeting outcomes will be documented and available to study staff.

Specific responsibilities of Investigators

1. *Awaiting approval.* An Investigator may determine whether potential subjects would be interested in participating in an investigation, but shall not request the written informed consent of any subject to participate, and shall not allow any subject to participate before obtaining IRB approval.
2. *Subject Qualification.* The Investigator is responsible for ensuring that all subjects entering the study conform to the patient selection criteria.
3. *Compliance.* An Investigator shall conduct an investigation in accordance with the signed agreement with the Sponsor, the investigational plan, all applicable FDA regulations, and any conditions of approval imposed by an IRB or FDA.

Investigator Records

A participating Investigator shall maintain the following accurate, complete, and current records relating to the Investigator's participation in an investigation for a period of 3 years after completion of the study:

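### The exclusion criteria in 3.6.6 omit breastfeeding and prior non-allergic reactions, both of which section 4.4 lists as contraindications to fluorescein

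*Protocol*

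**What the plan says.** Protocol section 4.4, which sets out contraindications for use in this study, states "Administration of Fluorescein is contraindicated in patients with" and then gives two bullets: "Known allergy or prior adverse reaction to Fluorescein" and "Women who are pregnant or breastfeeding".

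Protocol section 3.6.6 lists six exclusions. Two concern the same ground: "History of allergy to FS" and "Pregnant women". The other four are age under 18, renal failure, inability to consent, and being a prisoner or inmate.

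On screening, section 3.6.4 says "Each potential participant will be assessed against the inclusion and exclusion criteria". Section 7.2 repeats this and adds "Investigators will determine if patients are eligible for the study during clinic appointments". Neither section refers to 4.4. Section 3.6.11, item 3, then has patients receive intravenous fluorescein (FS) when the tumor is exposed.

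**The concern.** The list that decides who enters the study is narrower than the list of people who must not receive the study drug. Section 3.6.6 takes up half of each bullet in 4.4 and leaves out the other half. It does not keep drug contraindications out of the eligibility list on principle, since it already includes FS allergy and pregnancy. The gap therefore looks like an oversight.

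What is at stake is patient safety. If 4.4 is overlooked at the clinic visit, a breastfeeding woman can be consented and dosed against the protocol's own contraindication. If 4.4 is remembered only in theatre, she has been consented for a study she cannot take part in. Keeping her eligible gains nothing in return.

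**Working it through.** **Comparison of the two lists**

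| Condition in 4.4 | Corresponding exclusion in 3.6.6 | Match |
|---|---|---|
| Known allergy | FS allergy | Yes |
| Prior adverse reaction | FS allergy only | In part: allergic reactions only |
| Pregnancy | Pregnancy | Yes |
| Breastfeeding | None | No |

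Of four conditions, two match, one is covered in part and one is absent. No other section of the protocol excludes breastfeeding women or patients with a prior non-allergic reaction.

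**Path of a breastfeeding patient through the text**

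1. She meets 3.6.5 if she has a suspected eligible tumor and an indication for microsurgery.
2. None of the six exclusions in 3.6.6 applies to her.
3. Sections 3.6.4 and 7.2 test her against those criteria only, so she can be consented.
4. Section 3.6.11 has her given FS, which 4.4 forbids.

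**Does excluding her lose data?** Section 6 says that imaging needs a fluorescent agent. Section 3.6.7 counts a patient in the study population only after YE560 visualization. A patient who may not receive FS therefore cannot contribute, whichever list is used.

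**Size of the prior-reaction part**

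Inputs from section 3.2: respiratory reactions 1 in 3,800, cardiac events 1 in 5,300, tonic-clonic seizure 1 in 13,900, together stated as 1 in 1,900. Input from section 3.5: up to 95 patients enrolled.

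- Check of the stated total: 1/3,800 + 1/5,300 + 1/13,900 = 0.000524, or 1 in 1,909. This agrees with the protocol.
- Assumption: a share *s* of the 95 had one earlier FS dose. The protocol does not give *s*; the range used is 10% to 100%.
- Expected number with a prior severe reaction = 95 × *s* / 1,900. For *s* = 100% this is 0.05; for *s* = 10% it is 0.005.
- Chance of at least one = 1 − (1 − *s*/1,900)^95. For *s* = 100% this is 4.9%; for *s* = 10% it is 0.5%.
- Some respiratory reactions may be allergic, and 3.6.6 would already exclude those. With cardiac events and seizures only, the rate is 1/5,300 + 1/13,900 = 0.00026. At *s* = 100% that gives 95 × 0.00026 = 0.025 expected and a 2.4% chance of at least one.

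Prior nausea is not counted. No figure is computed for breastfeeding, because the protocol gives none.

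**The case against.** The best reply is that the two sections do different jobs: 3.6.6 governs enrolment and 4.4 governs administration. Nothing in 3.6.6 permits dosing a breastfeeding woman, and Appendix 2, item 3 states "An Investigator shall conduct an investigation in accordance with the signed agreement with the Sponsor, the investigational plan", so 4.4 binds the investigator and could be applied at the clinic visit. On this reading the protocol as a whole already bars these patients, and harm requires someone to breach an express contraindication. That is right as far as it goes, and it is a main reason the point is minor. It does not remove the mismatch: the list named for screening is the more permissive one, and it does not send the reader to the stricter one.

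A second safeguard is that section 7.3 has the anaesthesiologist prepare and give FS according to the product insert. That section speaks of dosage and administration, and the insert's position on breastfeeding is not in the protocol, so this is partial mitigation at most. The consent form is not in the reviewed text, so whether it asks about breastfeeding is unknown.

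The prior-reaction part is fairly criticised as weak. The allergy exclusion covers the allergic reactions, the remainder is very rare, and the 4.9% is a ceiling that assumes every patient had FS before and includes respiratory reactions that may be allergic. All of that stands, and breastfeeding carries the point.

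Lastly, the phrase in 4.4 on prior adverse reactions, read literally, includes nausea. Copying it into 3.6.6 does not widen what 4.4 already bars.

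**Conclusion.** The concern holds as a minor inconsistency. Section 3.6.6 omits one contraindication in 4.4 (breastfeeding) and covers another only in part (prior adverse reaction). A breastfeeding woman passes every written eligibility step for a drug that 4.4 forbids her. Her protection then rests on 4.4 being applied separately.

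The breastfeeding gap is plain from the text and needs no assumption; how many patients it would touch is unknown, probably few. The prior-reaction gap is very small: at most 0.05 expected patients among 95, given the rates in section 3.2 and an assumed single earlier dose in every patient. No endpoint, estimate, error rate or sample size is affected.

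**What to change.** In Protocol section 3.6.6, make two changes:

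- replace the pregnancy exclusion with *Pregnant or breastfeeding women*;
- replace the allergy exclusion with *History of allergy or prior adverse reaction to FS*.

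Leave the other four exclusions and section 4.4 as they are. Sections 3.6.4 and 7.2 then need no edit, because the list they rely on will be complete.

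The cost is two phrases in an amendment. The new wording excludes only patients whom 4.4 already bars from FS, so recruitment of usable patients is unchanged.

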3.6.7. Point of Enrollment

Potential subjects will be provided with plain language information about the research on the informed consent form, prior to signing the consent form indicating their willingness to participate. The point of

enrollment shall be upon clinical evaluation and consent for surgery. The patient shall be considered as part of the study population once they have undergone the YE560 visualization during the indicated microsurgery with confirmatory histopathology. Patients will be withdrawn from the study population if their final histopathology is not consistent with vestibular schwannoma; this is expected to occur in less than 5% of subjects. Clinical data, intraoperative images, survey results and postoperative clinical data will still be maintained for these patients for potential case presentation or evaluation of bias.

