The hypothesis is that FS and YE560 may be used as a supplementary visualization aid to better distinguish the tumor from healthy nerve tissue and secondarily improve conservation of facial and hearing nerve function and attainment of gross total resection (GTR). Use of intravenous FS has FDA approval for ophthalmologic applications and its safety profile is well documented (Yanuzzi 1986). There have been studies demonstrating uptake of FS by VS tissue in vitro (Perez 2018). Additionally, the feasibility and utility of intraoperative fluorescence from FS intravenous administration and use of YE560 have been demonstrated with peripheral schwannomas in vivo (Pedro 2019). The YE560 fluorescence module available for the KINEVO 900 will be used to visualize fluorescein-stained tissue in yellow light. FS will be administered upon initial visualization of the VS. Utility of FS and YE560 will be assessed via surgeon survey, correlation with biopsy of fluorescent VS tissue, and color image analysis of healthy and VS tissue using the YE560.

A total of 90 consenting patients, either male or female, clinically indicated for resection of a suspected VS will be enrolled into the study. No exclusions will be made for recurrent VS following stereotactic radiosurgery or microsurgical resection or VS associated with neurofibromatosis type 2 (NF-2).

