3.1. Objectives

Primary objective of this initial feasibility study is to evaluate the benefit of using YE560 to visualize fluorescein sodium (FS) during surgery of VS, Meningioma, HNP, or HNS, determined from surgeon assessment.

Secondary objectives are:

- To evaluate the optimum FS dose and timing to be used with the YE560 device as determined by reported performance on surgeon surveys
- Quantify tissue differentiation of fluorescent VS and adjacent nerves using RGB image analysis
- To report clinical outcomes, including GTR rates, postoperative hearing outcomes, and postoperative facial nerve function

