3.4. Hypothesis

12. Given prior evidence of preferential uptake of FS in VS and meningiomas due to disrupted blood brain barrier, we hypothesize that use of intravenous FS will allow for visual differentiation of tumor and surrounding structures and nerves using YE560.
13. The optimal dosing for FS has not been established for this application. Pedro et al utilized 0.5-1.0 mg/kg body weight to visualize peripheral nerve sheath tumors with YE560. The authors found saturation of all tissues with 3-4 mg/kg dose within 18 seconds of administration. The blood-brain barrier may play a modulating role. Schebesch et al (2013) used 3-4 mg/kg to visualize malignant gliomas and observed fluorescence after 20-30 minutes. We suspect that the optimal dose will be 3-4 mg/kg, and peak fluorescence will take a similar amount of time. However, we will initially utilize 1.0 mg/kg SF administered at the time of first visualizing the tumor to enable subsequent doses (up to a maximum of 500 mg or 7 mg/kg). This will allow us

to determine the minimum effective dose and observe the time to peak fluorescence. The optimal dosing strategy will be finalized after the first 10 cases.

14. We hypothesize that the surgeons will be satisfied with the use of SF and YE560, as reflected in responses on the Surgeon Survey. Specifically, we hypothesize that greater than 75% of surgeons would choose to use SF and YE560 at least in the majority of future VS, meningioma, HNP, or HNS resections based on responses from the Surgeon Survey. Secondarily, we hypothesize that surgeons will rate the correlation of fluorescence with visual assessment with white light microscopy and electrostimulation to be “good” or “excellent” for over 75% of the cases.
15. Because the yellow fluorescence is primarily comprised of red and green components, we hypothesize that RGB component analysis of intraoperative images will yield significantly higher red and green values in the VS compared to the facial and cochlear nerves. Similar analysis may be conducted between the tumor and surround nerves or structures of interest for meningiomas, HNP, and HNS.

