3.5. Design and Proposed Analysis

16. The feasibility study will involve 90 patients, focusing on intra-operative visualization of fluorescein using YE560 in VS, meningioma, HNP, or HNS, inclusive of recurrent tumors, previously radiated tumors, and patients with neurofibromatosis type 2. There will be an allowance to enroll up to 95 patients to meet the goal of 90 subjects if subjects are withdrawn from the study due to a different pathologic entity diagnosed on biopsy of the tumor. Establishing the optimal dose and timing for FS will be a part of the feasibility study. Flexibility will be allowed with the dose and timing to achieve optimal visualization condition based on surgeon feedback with a maximum cumulative dose of 500 mg (standard dosage for ophthalmology angiography). The study will be largely descriptive, documenting the macroscopic appearance of FS and describing surgeon observations with regards to timing of peak fluorescence, correlation with electrostimulation, and utility in differentiating normal tissue from tumor.
17. Images containing the tumor and facial and cochlear nerves (or other relevant structures of interest in the case of meningioma, HNP, or HNS) will be captured with the microscope with the YE560 filter by the surgeon and analyzed; the YE560 filter will then be turned off and another identical image will be captured under white light microscopy for the separate survey validation analysis. For the RGB component image analysis, the fluorescence of the tumor will be measured in comparison to the facial nerve and cochlear nerve using ImageJ image analysis software to quantify the red, green, and blue components of the images. Inferential statistics will be used to compare the red, green, and blue components of regions of interest from the VS and the adjacent facial or cochlear nerve.
18. For the survey validation analysis, we will validate the question “How well did fluorescence correlate with your visual assessment of the tumor and nerve tissue under normal microscopy without the Yellow 560 filter?” The neurosurgeons and neurologists will be presented with 30-60 second videos of the VS and facial and/or cochlear nerves, with and without YE560 active. The surgeons will respond to the above question with choices of “no correlation,” “some

correlation,” “good correlation,” and “excellent correlation.” Other questions from the surgeon survey will not be validated due to the scope of the feasibility study.

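### Sections 3.6.7 and 7.2 withdraw every patient whose tumour is not a vestibular schwannoma, although the protocol enrols, counts and plans to analyse four tumour types

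*Protocol*

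**What the plan says.** Two sections define withdrawal by VS alone.

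- Protocol 3.6.7: "Patients will be withdrawn from the study population if their final histopathology is not consistent with vestibular schwannoma". It expects this in under 5% of subjects. Data on withdrawn patients are kept, but only for possible case presentation or to assess bias.
- Protocol 7.2: "Participants will be withdrawn if their intraoperative biopsy yields an entity other than VS".

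Two sections describe the population itself as VS-only. Section 1.3 says that 90 consenting patients "clinically indicated for resection of a suspected VS will be enrolled into the study", although the purpose stated at the start of that section names all four tumours. Section 7.2 says that patients "clinically indicated for surgical resection as a suspected VS or recurrent VS will be considered eligible for participation in the study".

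The rest of the protocol describes a four-tumour study.

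- 3.1, primary objective: "to evaluate the benefit of using YE560 to visualize fluorescein sodium (FS) during surgery of VS, Meningioma, HNP, or HNS".
- 3.4, hypothesis: more than 75% of surgeons would choose the technique "at least in the majority of future VS, meningioma, HNP, or HNS resections based on responses from the Surgeon Survey".
- 3.5, design: "The feasibility study will involve 90 patients, focusing on intra-operative visualization of fluorescein using YE560 in VS, meningioma, HNP, or HNS". Enrolment may rise to 95 to reach 90 "if subjects are withdrawn from the study due to a different pathologic entity diagnosed on biopsy of the tumor".
- 3.6.2 applies the same target of 90 to all four tumours, and 3.6.5 makes all four eligible.
- 3.6.9 plans a separate image analysis for the tumour types other than VS.

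Section 3.6.11, item 11, withdraws lesions whose histology is excluded from the study. It does not name the entities, and the exclusion criteria in 3.6.6 list no histology.

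**The concern.** A patient with confirmed meningioma is eligible, counts toward the 90 and has a planned analysis, and must also be withdrawn. The same holds for HNP and, as a schwannoma that is not vestibular, for HNS.

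What is at stake is the study population. The primary outcome in 3.6.8 is a percentage of survey responses compared with 75%. Under one reading its denominator covers four tumours, under the other only VS. These answer different questions, and the protocol does not say which one it asks. If the choice is left until the responses are known, the reported percentage and the tumours it describes can depend on that choice.

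The two VS-only rules also use different triggers: final histopathology in 3.6.7 and intraoperative biopsy in 7.2. The protocol does not say which governs when they disagree.

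**Working it through.** **Inputs**

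- Target 90 and enrolment cap 95 (3.5).
- Expected withdrawal under 5%, stated for histology that is not VS (3.6.7).
- Share *s* of enrolled patients whose tumour is not VS: not stated, so shown as an assumed range.

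**Step 1. Reproduce the cap.** Enrolment needed = 90/(1 − withdrawal rate). With 5%: 90/0.95 = 94.7, rounded up to 95. Conversely, 95 × 0.95 = 90.25, so 90 is met. The cap and the rate agree with each other.

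**Step 2. What the cap tolerates.** 95 − 90 = 5 withdrawals, and 5/95 = 5.3%. If every non-VS patient is withdrawn, 90 is reached only when meningioma, HNP, HNS and all other entities together make up no more than 5 of 95 enrolled.

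**Step 3. Larger non-VS shares under the VS-only rule.** Retained = 95 × (1 − *s*); enrolment needed to keep 90 = 90/(1 − *s*).

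| Assumed *s* | Retained of 95 | Enrolment needed for 90 |
|---|---|---|
| 10% | 85.5 (about 85) | 100 |
| 25% | 71.25 (about 71) | 120 |
| 50% | 47.5 (about 47) | 180 |

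**Step 4. The two readings side by side.**

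| Element | Withdraw all non-VS (3.6.7, 7.2) | Withdraw only histology outside the four |
|---|---|---|
| Objective, hypothesis, eligibility (3.1, 3.4, 3.6.5) | contradicted | consistent |
| Target of 90 over four tumours (3.5, 3.6.2) | contradicted | consistent |
| Analysis of other tumour types (3.6.9) | no study population | possible |
| Cap of 95 with about 5% withdrawal | works only if non-VS is at most 5.3% | works if the rate holds for histology outside the four |
| VS-only population text (1.3, 7.2) | consistent | contradicted |

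Neither reading agrees with every section. Most of the text supports the second.

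**The case against.** The strongest reply is that this is leftover wording from a VS-only study and that the intended rule is plain. Much of that stands. In 3.5, the withdrawal for a different pathologic entity follows directly on a list of the four tumours, so it naturally means none of those four. Item 11 of 3.6.11 reads the same way against the inclusion criteria. These passages point to the likely intent. But they do not override two explicit VS-only sentences, and 1.3 and 7.2 repeat the narrower population. Intent does not tell study staff whom to withdraw.

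A second reply is that no data are lost. That is correct as to records. The other-tumour analysis could be run on the retained images, and 3.4 describes a similar analysis only as something that may be done. However, 3.6.7 limits the stated use of the retained data and places these patients outside the study population.

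A third concerns HNS. Section 3.2 calls benign peripheral nerve sheath tumours histologically identical to VS, so one could argue that an HNS is still consistent with VS under 3.6.7. The test in 7.2, an entity other than VS, is harder to read that way. The conflict for meningioma and HNP does not depend on this.

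Four stronger readings are tempting, and the document does not support them.

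- A reader might infer that withdrawing one patient could by itself carry the primary percentage across 75%. Section 3.5 allows withdrawn patients to be replaced up to 95, and more than one survey response per case is possible, so a simple one-patient change of denominator is not a fair illustration.
- A reader might take the under-5% figure as a limit on non-VS patients. It is an expectation.
- A reader might conclude that the cap was miscalculated. Step 1 shows that it was not; the question is which rule it belongs to.
- A reader might conclude that only descriptive results are touched. The study is largely descriptive and 3.6.8 sets no decision rule for the primary outcome, but 3.5 also plans inferential comparisons of the image components, and 3.6.9 extends similar analysis to the other tumours.

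**Conclusion.** Wrong as written: an internal inconsistency, not a design choice. Sections 3.6.7 and 7.2 remove patients whom 3.1, 3.4, 3.5, 3.6.2, 3.6.5 and 3.6.9 include, and nothing in the protocol resolves the conflict. The denominator of the primary outcome is therefore not fixed, and on the literal rule the other-tumour analysis has no study population.

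The size of the loss cannot be computed, because the tumour mix is not stated. The protocol's own figures fix only the boundary: under the VS-only rule, 95 enrolled yields 90 if at most 5 (5.3%) are not VS. The retained numbers of about 85, 71 and 47 rest on assumed non-VS shares of 10%, 25% and 50% and are not predictions. The need for correction rests on the undefined population and not on any one of these shares.

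**What to change.** 1. Replace the withdrawal sentences in 3.6.7 and 7.2 with one rule: a patient leaves the study population only if the histology is none of VS, meningioma, HNP or HNS. This is how 3.5 and item 11 of 3.6.11 naturally read. If a VS-only study is intended instead, restrict the objective, hypothesis, eligibility, target and analyses to VS.
2. Name one governing histology trigger, final histopathology or intraoperative biopsy, and use it throughout.
3. Align the VS-only population text in 1.3 and 7.2 with the choice made.
4. Confirm that the under-5% expectation, which 3.6.7 gives for non-VS histology, and the cap of 95 apply to the rule chosen.

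The cost is a wording amendment and confirmation of one figure. More patients are needed only if the expected withdrawal share under the chosen rule exceeds 5/95 (5.3%), in which case the cap would have to rise.
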